6.9.1. Duration of Follow Up

Long-term follow up will include an assessment for disease progression in subjects who did not progress during treatment. This should occur every 3 months (+/- 30 days) for up to 6 years from enrollment.

6.10. Safety Considerations & Supportive Care

Supportive measures for optimal medical care shall be provided during participation in this clinical trial. Supportive care including anti-nausea / anti-emetic therapy, acid suppression (proton pump inhibitors and/or H2-blockers), glucocorticoids, and other standard treatments may be administered as per institutional guidelines for symptomatic subjects. As needed and per individual study site institutional guidelines, prophylactic therapies, including antivirals, antifungals, and antibiotics, may be administered to ameliorate risks associated with non-malignant disorders or of immune system compromise.

6.10.1. Elotuzumab Infusion Reactions

The first dose of elotuzumab will be administered following pre-medications to each subject as an IV infusion, using an automated infusion pump set at an initial rate of 0.5mL per minute (30 mL/hour). If the subject does not have an infusion reaction within 30 minutes, escalate the infusion rate by 0.5 mL per minute. If the subject still does not have an infusion reaction within 30 minutes, escalate the infusion rate to a maximum of 2 mL per minute (120 mL/hour).

The second dose of elotuzumab should be initiated at an infusion rate of 3 mL per minute if no infusion reactions were reported with the first elotuzumab infusion. If the subject does not experience an infusion reaction during the first 30 minutes of the second dose of elotuzumab, escalate the infusion rate by 1.0 mL per minute to a maximum infusion rate of 4 mL per minute.

The third and fourth dose of elotuzumab should be initiated at an infusion rate of 5 mL per minute if no infusion reactions were reported with previous elotuzumab infusions.

Guidelines for Elotuzumab Infusion in Subjects with Infusion Reactions

Grade 1 Infusion Reaction: Grade 1 elotuzumab infusion-related reactions by definition do not require intervention; however, increased monitoring is recommended

Grade 2 or 3 Infusion Reaction: Infusion reactions during the elotuzumab infusion: For a Grade 2 or 3 elotuzumab infusion-related reactions, the infusion must be interrupted. The subject should be treated as clinically indicated with one or more of the following medications or

interventions: antiemetics, antihistamines, analgesics, corticosteroids, leukotriene inhibitors, oxygen inhalation, epinephrine, bronchodilators, or other supportive measures as indicated.

Once the elotuzumab infusion-related reaction has resolved to Grade ≤ 1 , the infusion can be restarted at 0.5 mL/minute. If symptoms do not recur after 30 minutes, the infusion rate may be increased in a stepwise fashion (0.5 mL/minute every 30 minutes) to the rate at which the infusion reaction occurred. If no recurrence of the infusion reaction, the escalation regimen can be resumed. Subjects who experience an infusion reaction require vital signs to be monitored every 30 minutes for 1 or 2 hours after the end of the elotuzumab infusion (as clinically indicated). If the elotuzumab infusion reaction recurs, the infusion must be stopped and not restarted on that day. Appropriate therapy should be administered to address the subject's signs and symptoms. The infusion can be reattempted at the next protocol defined infusion time point at the investigator's discretion with additional premedication.

Infusion reactions after the completion of elotuzumab infusion: Should a Grade 2 or 3 infusion reaction occur following the completion of an elotuzumab infusion, the subject should be treated as clinically indicated with 1 or more of the following medications or interventions: diphenhydramine, acetaminophen, hydrocortisone, H2 inhibitor, leukotriene inhibitor, oxygen inhalation, epinephrine, bronchodialators, or other supportive measures as indicated.

Elotuzumab infusions on subsequent weeks after a prior Grade 2 or 3 infusion reaction: Subjects with a prior Grade 2 or 3 infusion reactions should have the next infusion started at 0.5 mL/min and then escalated in a stepwise fashion (0.5 mL/minute every 30 minutes) to the rate at which the infusion reaction occurred. If no Grade ≥2 infusion reaction occurs, the escalation regimen may be resumed, and the next infusion may be initiated as planned per regimen.

Grade 4 Infusion Reaction: Subjects with a Grade 4 elotuzumab infusion reaction must have elotuzumab permanently discontinued.

6.10.2. First Dose Effect (Carfilzomib)

A "first dose effect" has been seen, which is notable for fever, chills, rigors, and/or dyspnea occurring during the evening following the first day of infusion and an increase in creatinine on Day 2, which may be the clinical sequelae of rapid tumor lysis and/or cytokine release.

All subjects should be well hydrated (Section 6.3.2). Clinically significant electrolyte abnormalities should be corrected prior to dosing with carfilzomib. Renal function must be monitored closely during treatment.

Should a "first dose" effect occur at any point during Cycle 1 or 2, treatment with high dose glucocorticoids (e.g. methylprednisolone 50–100 mg) is recommended. In addition, intravenous fluids, vasopressors, oxygen, bronchodilators, and acetaminophen should be available for immediate use and instituted, as medically indicated.

6.10.3. Tumor Lysis Syndrome

TLS, which may be associated with multi-organ failure, has been observed in treatment Cycles 1 and 2 in some subjects with MM who have been treated with carfilzomib. All subjects should follow the hydration guidelines outlined in Section 6.3.2. If subjects are considered to be at risk for TLS, hydration should be continued into Cycle 2 if clinically indicated.

MM subjects with high tumor burden (e.g., Durie-Salmon or ISS Stage II/III), rapidly increasing M-protein or light chains, or compromised renal function (CrCl < 50 mL/min) should be considered to be at particularly high risk.

During Cycles 1 and 2, serum electrolytes and chemistries are closely monitored. Subjects with laboratory abnormalities consistent with lysis of tumor cells (e.g. serum creatinine $\geq 50\%$ increase, LDH \geq 2-fold increase, uric acid $\geq 50\%$ increase, phosphate $\geq 50\%$ increase, potassium $\geq 30\%$ increase, calcium $\geq 20\%$ decrease) prior to dosing should not receive the scheduled dose. Subjects with such abnormalities should be re-evaluated as clinically indicated. The Lead Principal Investigator should be consulted if there are further delays.

If TLS occurs, cardiac rhythm, fluid, and serial laboratory monitoring should be instituted. Correct electrolyte abnormalities, monitor renal function and fluid balance, and administer therapeutic and supportive care, including dialysis, as clinically indicated.

All cases of TLS must be reported to the Lead Principal Investigator (who will, in turn be responsible for distributing this information to all sites) and to Amgen as a Serious Adverse Event (SAE) through the normal process within 24 hours of the clinical site becoming aware of the event.

6.10.4. Renal Function

Carfilzomib has not been fully characterized in subjects with creatinine clearance < 30 mL/min. It is critical that the subject's renal function is known at the time of dosing. Renal function, serum creatinine, and serum uric acid should be monitored closely during treatment with carfilzomib. Renal function must be monitored closely during treatment with carfilzomib. Serum chemistry values, including creatinine, must be obtained and reviewed prior to each dose of carfilzomib during Cycles 1 and 2. Refer to Table 6-7 for guidance regarding dose reduction in subjects with compromised renal function.

7. SAMPLES FOR MRD EVALUATION AND CORRELATIVE STUDIES

Bone marrow samples for MRD evaluation are required and as per the standard of care and will be collected prior to initiation of treatment (screening), at the completion of 4 (non-SOC for subjects who do not continue to ASCT), 8, 12, and 18 (for subjects who are MRD+ at the end of C8 but MRD- at the end of C12 only) cycles of E-KRd, 24 months after C1D1 for all subjects, and then yearly or at the time of near complete response (nCR determination is not possible, then VGPR will be used to trigger a bone marrow biopsy. A Bone Marrow Biopsy to confirm nCR or VGPR will not be required if the subject is within 2 months of a landmark BMBX timepoint) if more than 2-3 months from scheduled evaluation, and/or progression/relapse.

MRD evaluation will be done centrally at the University of Chicago (by Flow) and at Adaptive Biotechnologies (by NGS). For this purpose, two BM samples must be shipped at each timepoint.

Additionally, provided that the subject consents, correlative samples will be collected and banked for further research studies.

Shipping locations will be as follows:

Samples Shipped to University of Chicago Hematology Lab:

Screening, cycle 4, cycle 8, cycle 12, cycle 18 (when applicable), 24 months after C1D1, yearly after that, and at the time of nCR (or VGPR if nCR determination is not possible)

Samples Shipped to Adaptive Biotechnologies directly:

- End of cycle 12 for quick turnaround for treatment decision

Samples Shipped to University of Chicago MM lab:

- Screening, cycle 4, cycle 8, cycle 18 (when applicable), 24 months after C1D1, yearly after that,, and the time of nCR, or VGPR when nCR determination is not possible (MRD only for batch shipping to Adaptive)
- Screening, cycle 4, cycle 8, cycle 12, cycle 18 (when applicable), 24 months after C1D1, and at the time of nCR, or VGPR when nCR determination is not possible (all correlative samples)

Shipment time points are outlined below.

Table 7-1 MRD and correlative sample shipment schema

MRD sample	Correlative Sample	Time Points	
Bone Marrow Aspirate	Bone Marrow Aspirate	Screening/Pre-treatment, after 4, 8 and 12, and 18 (when	
	Peripheral Blood	applicable) cycles, 24 months after C1D1,, yearly after that,	
	Plasma/Serum	and at the time of near complete response (or VGPR if nCR determination is not possible)	
Buccal Swab		Progression/Relapse* Screening only	

^{*} Correlative sample only

8. ADVERSE EVENTS

An Adverse Event (AE) is defined as any new untoward medical occurrence or worsening of a preexisting medical condition in a clinical investigation subject administered an investigational (medicinal) product and that does not necessarily have a causal relationship with this treatment. An AE can therefore be any unfavorable and unintended sign (such as an abnormal laboratory finding), symptom, or disease temporally associated with the use of investigational product, whether or not considered related to the investigational product.

Adverse events can be spontaneously reported or elicited during open-ended questioning, examination, or evaluation of a subject. (In order to prevent reporting bias, subjects should not be questioned regarding the specific occurrence of one or more AEs.)

NONSERIOUS ADVERSE EVENT

- Nonserious Adverse Events are to be provided to BMS in aggregate via interim or final study reports as specified in the agreement or, if a regulatory requirement [e.g. IND US trial] as part of an annual reporting requirement.
- Nonserious AE information should also be collected from the start of a placebo lead-in period or other observational period intended to establish a baseline status for the subjects.

A nonserious adverse event is an AE not classified as serious.

Nonserious Adverse Event Collection and Reporting

The collection of nonserious AE information should begin at initiation of study drug. All nonserious adverse events deemed to be related to study drug combination should be collected continuously during the treatment period and for a minimum of 30 days following the last dose of study treatment.

Nonserious AEs should be followed to resolution or stabilization, or reported as SAEs if they become serious. Follow-up is also required for nonserious AEs that cause interruption or discontinuation of study drug and for those present at the end of study treatment as appropriate.

Laboratory Test Abnormalities

All laboratory test results captured as part of the study should be recorded following institutional procedures. Test results that constitute SAEs should be documented and reported as such.

The following laboratory abnormalities should be documented and reported appropriately:

- any laboratory test result that is clinically significant or meets the definition of an SAE
- any laboratory abnormality that required the subject to have study drug discontinued or interrupted
- any laboratory abnormality that required the subject to receive specific corrective therapy.

Potential Drug Induced Liver Injury (DILI)

Wherever possible, timely confirmation of initial liver-related laboratory abnormalities should occur prior to the reporting of a potential DILI event. All occurrences of potential DILIs, meeting the defined criteria, must be reported as SAEs. Potential drug induced liver injury is defined as:

- 1) ALT or AST elevation > 3 times upper limit of normal (ULN) AND
- Total bilirubin > 2 times ULN, without initial findings of cholestasis (elevated serum alkaline phosphatase)
 AND
- 3) No other immediately apparent possible causes of AST/ALT elevation and hyperbilirubinemia, including, but not limited to, viral hepatitis, pre-existing chronic or acute liver disease, or the administration of other drug(s) known to be hepatotoxic.

Overdose

An overdose is defined as the accidental or intentional administration of any dose of a product that is considered both excessive and medically important. All occurrences of overdose must be reported as an SAE.

Other Safety Considerations

Any significant worsening noted during interim or final physical examinations, electrocardiograms, x-rays, and any other potential safety assessments, whether or not these procedures are required by the protocol, should also be recorded as a nonserious or serious AE, as appropriate, and reported accordingly.

Unexpected AEs

An unexpected AE is any adverse drug event, the specificity or severity of which is not consistent with the current IB or prescribing information for a marketed compound. Also, reports which add significant information on specificity or severity of a known, already documented AE constitute unexpected AEs. For example, an event more specific or more severe than described in the IB would be considered "unexpected".

Whenever possible, the Common Terminology Criteria for Adverse Events (CTCAE) version 4.0 should be used to describe the event and for assessing the severity of AEs (see Appendix 3). Any events representing a change in the CTCAE Grade need to be reported on the AE case report form. This includes any change in laboratory values.

For AEs not adequately addressed in the CTCAE, the severity table below may be us	For AEs r	ot adequately	addressed in	the CTCAE.	the severity	v table below may	v be used:
---	-----------	---------------	--------------	------------	--------------	-------------------	------------

Severity	Description
GRADE 1 – Mild	Transient or mild discomfort; no limitation in activity; no medical intervention/therapy required.
GRADE 2 – Moderate	Mild to moderate limitation in activity—some assistance may be needed; no or minimal medical intervention/therapy required.
GRADE 3 – Severe	Marked limitation in activity, some assistance usually required; medical intervention/therapy required, hospitalizations possible.
GRADE 4 – Life-threatening	Extreme limitation in activity, significant assistance required; life-threatening (immediate risk of death); significant medical intervention/therapy required, hospitalization or hospice care probable.
GRADE 5 – Fatal	Death

Any condition, laboratory abnormality, or physical finding with an onset date prior to the subject signing consent for study participation is considered to be pre-existing in nature and part of the subject's medical history.

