Safety Variables & Analysis	The safety and tolerability of elotuzumab, lenalidomide, and carfilzomib will be evaluated by means of drug related AE reports, physical examinations, and laboratory safety evaluations. Common Terminology Criteria for Adverse Events (CTCAE) V 4.0 will be used for grading of AEs. Treating Investigators will provide their assessment of causality as 1) unrelated, 2) unlikely related 3) possibly related, or 4) probably or 5) definitely related for all AEs.	
Statistical Analysis	A total of 55 subjects will be enrolled in a single-stage Phase II design. Time to progression or death will be calculated from the date of first treatment on protocol until the date of disease progression or death from any cause. Subjects at the time of analysis not having either endpoint will be censored as of the last negative exam (tumor assessment). Adherence to protocol and ability to follow subjects in follow-up is expected to be excellent; however, if any subject revokes consent for further follow-up not due to disease progression, they will be censored as of the last negative exam. Likewise, subjects in follow-up that are lost or that refuse or revoke further study participation will be censored as of the last negative exam.	

Page 16

LIST OF ABBREVIATIONS AND DEFINITIONS OF TERMS

□C degrees Centigrade
□F degrees Fahrenheit
AE Adverse event

ALT Alanine aminotransferase
ANC Absolute neutrophil count
AML Acute myeloid leukemia

aPTT Activated partial thromboplastin time (also PTT)

ASaT All Subjects as Treated

ASCT Autologous Stem Cell Transplant
AST Aspartate aminotransferase

ASO-PCR Allele-Specific Oligonucleotide Polymerase Chain Reaction

bid Twice daily
BSA Body surface area
BUN Blood urea nitrogen
CBC Complete blood count
CFR Code of Federal Regulations
CHF Congestive heart failure

CK Creatinine kinase
CNS Central nervous system
CR Complete response
CrCl Creatinine Clearance
CRF Case report form(s)

CRM1 Chromosome region maintenance protein 1

CRO Clinical research organization

CSR Clinical Study Report

CTCAE Common Terminology Criteria for Adverse Events

CT Scan Computed Tomography Scan

CV Curriculum vitae CYP450 Cytochrome P450

dL Deciliter

DLT Dose-limiting toxicity
DNA Deoxyribonucleic acid
DOR Duration of response
DVT Deep venous thrombosis
EC Ethical Committee
ECG Electrocardiogram

ECOG Eastern Cooperative Oncology Group

EOT End of Treatment FAS Full Analysis Set

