8.2. Adverse Event Reporting Procedures

Information about all AEs, whether volunteered by the subject, discovered by the Treating Investigator questioning, or detected through physical examination, laboratory tests or other means, will be collected and recorded in eVelos and followed as appropriate.

All Adverse Events **must** be reported in routine study data submissions to the lead PI who will review and will be responsible for alerting all participating sites about the AE as required. **AEs reported using the Serious Event Reporting Form and/or MedWatch Form discussed below must also be reported in routine study data submissions in eVelos. Details of the event must include severity, relationship to study drug, duration, action taken, and outcome as shown on the eCRF in eVelos. All AEs must be followed to resolution or stabilization regardless of relationship to study drug.**

All AEs that are considered related to study regimen must be followed to resolution or stabilization if improvement is not expected.

AEs must be reported from the date of the first dose of treatment through 30 days post-last dose of study treatment or initiation of a new anti-cancer therapy, whichever occurs first. If a subject is enrolled but discontinues study prior to receiving any study drug, only SAEs that are considered related to study procedures must be reported through the end-of-study visit. AEs that completely resolve and then recur should be recorded as a new AE. For subjects who complete the end of study visit less than 30 days following their last dose of study drug, a follow up of ongoing AEs should be attempted by telephone, and documented in the subject's source. AEs continuing at 30 days post-last dose should have a comment in the source by the Treating Investigator that the event has stabilized or is not expected to improve. SAEs continuing at 30 days post-last dose should be followed until resolution or stabilization.

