10.2.1. Primary Objective Sample Size Justification

The primary endpoint is the sCR rate and/or the rate of MRD-negativity after 8 cycles of therapy. The rate of sCR for KRd treatment is established as the primary reference endpoint for statistical considerations by robust data (Jakubowiak et al., 2012b) Recognizing that the measurement of sCR has technical challenges when involving elotuzumab – which are anticipated to be resolved by the time it is needed – a co-primary endpoint of MRD-negative status by NGS is included in the primary efficacy assessment. This is based on the close correlation between MRD-negative status and sCR rate established in the ongoing KRd+transplant study (Jakubowiak et al. EHA 2016, Zimmerman et al. ASH 2016, both oral presentations). This primary endpoint incorporates also the new definition of MRD status, which requires sCR to confirm MRD negativity (Kumar et al., 2016). Therefore, an improvement from historical 30% (which is the sCR rate and the estimated MRD-negative rate by NGS in the KRd study without elotuzumab (Jakubowiak, 2016)) to 50% or higher sCR and/or MRD-negative status at the completion of 8 cycles, would be considered promising.

For 40 non-transplant candidates and/or transplant candidates who agreed to defer transplant, we will test the null hypothesis that the sCR and/or negative MRD status by NGS rate after 8 cycles is, \leq 30% against the alternative that it is, \geq 30% using an exact one-sided binomial test at the alpha=0.10 significance level. The null hypothesis will be rejected if 17 or more sCR's and/or MRD-negative's responses are observed (\geq 42.5%). The sample size of n=40 response evaluable subjects provides a little over 85% power if the true sCR and/or negative MRD status rate by NGS is 50%. The sample size is selected to also allow for collection of sufficient data for toxicity and tolerability evaluation of the E-KRd regimen. The frequency of adverse events will be summarized by type, grade, and attribution to the study drugs.

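### Section 8 asks for non-serious AEs judged drug-related, Section 8.2 asks for all AEs, and nothing says which rule governs

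*Combined protocol and SAP*

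**What the plan says.** Section 8 defines an AE independently of causality, "whether or not considered related to the investigational product". Further on, under the heading for non-serious AE collection and reporting, it sets a narrower rule: "All nonserious adverse events deemed to be related to study drug combination should be collected". That rule runs through treatment and for at least 30 days after the last dose.

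Section 8.2 is broader. "Information about all AEs, whether volunteered by the subject, discovered by the Treating Investigator questioning" or found by examination or laboratory test is to be collected and entered in eVelos. All AEs must appear in routine data submissions, and "All AEs must be followed to resolution or stabilization regardless of relationship to study drug".

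The synopsis, in its row on safety variables and analysis, says safety will be assessed by "means of drug related AE reports, physical examinations, and laboratory safety evaluations". The same row asks treating investigators to grade causality, on a scale that includes unrelated, for all AEs.

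Section 10.2.1 gives the planned analysis in one sentence: "The frequency of adverse events will be summarized by type, grade, and attribution to the study drugs". It does not say whether the tabulation is all-cause or restricted to related events.

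**The concern.** Two collection rules cover the same non-serious events over nearly the same period, and they differ on whether the investigator's causality opinion decides if an event is recorded. The trial has one open-label arm and a four-drug regimen. The treating investigator therefore attributes events unblinded, and there is no concurrent control against which misattribution would show. An event never entered cannot be re-attributed later.

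Safety carries real weight here. Section 3.2 lists AE rate, classification and relation to study drug as a secondary endpoint, and Section 4.1 mentions safety and tolerability in its primary endpoint statement. Section 10.2 plans 15 of the 55 subjects (15/55 = 27%) to add tolerability and toxicity data.

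**Working it through.** The plan states no figure on this point, so the check is a comparison of texts, followed by an illustration on assumed values.

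**Step 1. What each place requires**

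| Place | Filter on relatedness? |
|---|---|
| Section 8, AE definition | No |
| Section 8, non-serious collection rule | Yes: related events named |
| Section 8, other safety considerations (significant worsening) and CTCAE grade changes | No |
| Section 8.2, recording in eVelos and routine submission | No |
| Section 8.2, grade 3-4 laboratory abnormalities | No: all recorded |
| Section 8.2, grade 1-2 laboratory values | Partly: clinical significance, relatedness and/or need for medication |
| Section 6.2.1 and Appendix 6 note 18 | No |
| Sections 8.3.1 and 8.4, SAEs | No: reported whether or not related |
| Synopsis, basis of the safety evaluation | Yes: drug-related reports |
| Synopsis, causality assessment | No: all AEs |
| Section 10.2.1, tabulation | Not stated |

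**Step 2. Does any text settle it?** No passage gives Section 8 or Section 8.2 precedence. Section 8.1 has five causality levels, but nothing says which count as related for the Section 8 rule. The nearest text, also in 8.1, keeps every AE in dose-limiting toxicity evaluation unless it is clearly unrelated, and is not tied to collection. Two sites could treat an event graded unlikely in opposite ways, and each could point to the protocol.

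**Step 3. What is lost if Section 8 is followed literally?** From Step 1, SAEs and grade 3-4 laboratory abnormalities stay in. What can drop out is a non-serious event, mainly non-laboratory, that the investigator judges unrelated.

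**Step 4. Illustration of scale (assumed values only).** The documents give no attribution rates. Let p be the true all-cause incidence of one type of non-serious event and s the share attributed to study drug. Assume one episode per affected subject and that every site follows Section 8. Then captured incidence = p × s.

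| p | s = 90% | s = 70% | s = 50% |
|---|---|---|---|
| 10% | 9% | 7% | 5% |
| 30% | 27% | 21% | 15% |
| 50% | 45% | 35% | 25% |

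With 55 subjects and p = 30%, 55 × 0.30 = 16.5 subjects are expected. Captured counts are 16.5 × 0.9 = 14.85, 16.5 × 0.7 = 11.55 and 16.5 × 0.5 = 8.25. The shortfall shrinks as fewer sites follow Section 8 and is zero if none does. These figures show the mechanism; they do not estimate this trial's shortfall.

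**The case against.** The strongest reply is that the protocol, read as a whole, intends all AEs to be collected. Section 8.2 uses mandatory language, while the Section 8 sentence says should and contains no word such as only. The sentence just before it starts collection of non-serious AE information without a filter. The same part of Section 8 mentions a placebo lead-in period that this trial does not have, which suggests carried-over template text. A five-level causality scale and a tabulation by attribution make sense only if unrelated events are recorded. Sites also share one database, central training and central monitoring.

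Most of this stands as evidence of intent, and it makes the harm conditional on a site following Section 8. It does not remove the conflict. A sentence under a collection heading that names a subset to collect is naturally read as a limit, and a site that read it so would be following a written instruction.

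A reader might infer more than the text supports:

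- **That the synopsis limits collection.** It limits what is used to evaluate safety, is not specific to non-serious events, and asks for causality on all AEs.
- **That the unrelated categories would be empty.** Unrelated SAEs and unrelated grade 3-4 laboratory abnormalities would still be there.
- **That the overall AE rate falls by exactly the share judged unrelated.** Only non-serious events are exposed. A subject with several events stays in the any-AE count if one of them is judged related.
- **That a between-site comparison is damaged.** None is planned. The issue is what the pooled rate means.

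**Conclusion.** The conflict is real and unresolved: one stated rule filters non-serious AEs through unblinded attribution, another does not, and the analysis section does not say which set it tabulates. Where Section 8 is followed, the all-cause non-serious AE rate is understated. The direction is clear; the size cannot be estimated, because the documents give neither the share of events judged unrelated nor which rule sites use. SAEs, grade 3-4 laboratory abnormalities, and all sample size and power statements are unaffected. Attribution would remain unblinded after any rewording, so the correction protects the all-cause count and leaves the related count as subjective as in any open-label single-arm trial. The point is worth correcting because AE rate is a stated endpoint and the remedy is cheap.

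**What to change.** - In Section 8, remove the relatedness qualifier from the non-serious collection sentence so that it matches Section 8.2.
- In the synopsis, remove the restriction to drug-related reports from the description of the safety evaluation.
- In Section 10, state that AE frequencies are tabulated all-cause, with the related subset alongside, and define which of the five causality levels count as related.
- For data already collected, document which rule each site applied, and enter omitted events from source where possible.

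The amendment is wording only, since Section 8.2 already requires the data. The costs are back-entry at any site that followed Section 8 and somewhat higher reported AE rates.
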